8.3.4 TIME PERIOD AND FREQUENCY FOR EVENT ASSESSMENT AND FOLLOW-UP

Any medical condition that is present at the time that the subject is screened, but does not exclude said subject, will be considered as baseline and not reported as an AE. However, if the study subject's condition deteriorates at any time during the study, it will be recorded as an AE.

Changes in the severity of an AE will be documented to allow an assessment of the duration of the event at each level of severity to be performed. AEs characterized by surgeon to be intermittent, or having distinct episodes, require documentation of onset and duration of each episode.

An investigator will record all reportable events with start dates occurring any time after informed consent is obtained until the last day of study participation, AEs occurring before, but not resolving by, the last day of study participation will be followed for an additional 7 (for non-serious AEs) or 30 days

Protocol QD-PRO-045 Rev 005

(for SAEs) after. If such an SAE is determined to be probably or definitely related to the investigational device, then it may be followed for longer.

At each study visit, the investigator will inquire about the occurrence of AE/SAEs since the last visit. Events will be followed for outcome information until resolution or stabilization. All AEs will be followed to adequate resolution.

8.3.5 ADVERSE EVENT REPORTING

The PI or Site Coordinator shall complete an Adverse Event Form via the electronic data capture system for each adverse event.

The study Sponsor contact information is provided in Section 10.1.4, Key Roles. The study Sponsor is responsible for conducting an evaluation of an unanticipated adverse device effect and shall report the results of such evaluation to FDA as appropriate and to all reviewing IRBs and participating investigators within 10 working days after the sponsor first receives notice of the effect. Thereafter the sponsor shall submit such additional reports concerning the effect as requested by regulatory authorities.

8.3.6 SERIOUS ADVERSE EVENT REPORTING

Serious Adverse Events require completion of a Serious Adverse Event Report Form an investigator. Reported SAEs regardless of classification must be reviewed by study PI and reported as soon as possible, but in no event later than 10 working days after an investigator first learns of the event (§ 812.150(a)(1)).

The study investigator is also responsible for completing an Unanticipated Adverse Device Effect Form and submit to the study sponsor and to the reviewing Institutional Review Board (IRB) as soon as possible, but in no event later than 10 working days after the investigator first learns of the effect. The study sponsor is responsible for conducting an evaluation of an unanticipated adverse device effect and shall report the results of such evaluation to the Food and Drug Administration (FDA) and to all reviewing IRBs and participating investigators within 10 working days after the sponsor first receives notice of the effect. Thereafter, the sponsor shall submit such additional reports concerning the effect as FDA requests. See Section 10.1.4 for contact information.

All SAEs will be followed until satisfactory resolution or until the site investigator deems the event to be chronic or the outcome to be stable. Other supporting documentation of the event may be requested by the FDA or study sponsor and should be provided as soon as possible. The study sponsor will be responsible for notifying FDA of any unexpected fatal or life-threatening suspected adverse reaction as soon as possible but in no case later than seven calendar days after the sponsor's initial receipt of the information.

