- 8. Evidence of pelvic inflammatory disease (PID)
- 9. Known clotting defects or bleeding disorders
- 10. Hemoglobin < 8 g/dL
- 11. Metastatic disease
- 12. On anticoagulant therapy
- 13. Participation in another interventional trial
- 14. Pregnancy
- 15. Abnormal PAP results that have not been fully evaluated, or in the opinion of the investigator may indicate risk of abnormal vaginal cuff healing
- 16. Co-morbidities that, in the opinion of the investigator, may indicate risk of abnormal vaginal cuff healing

Intra-operative Exclusion Criteria

- 17. Bowel injury during laparoscopic hysterectomy procedure prior to attempted cuff closure
- 18. Bladder injury during laparoscopic hysterectomy procedure prior to attempted cuff closure
- 19. Cases in which surgeon cannot identify adequate tissue along the cuff to apply suture laparoscopically
- 20. Cases requiring conversion to laparotomy prior to study intervention

Description of Sites/Facilities Enrolling Participants:

The primary sites in this study will be:

Thomas Jefferson University Hospital with locations at [name] and [name]; and

Hershey Medical Center, Penn State College of Medicine at [name].

Enrollment may take place at any of these locations.

There may be additional sites within or outside the United States added (but not more than three total institutions), based upon enrollment.

Description of Study Intervention:

The Zip-stitch™ Vaginal Cuff Closure System is a surgical wound closure system consisting of a series of clips and a reusable, re-sterilizable clip applicator. The clips are made of the bio-absorbable polymer poly-p-dioxanone (PDO) and maintain closure of the vaginal cuff during the healing process, then are ultimately absorbed by the body five to eight months after application.

Protocol QD-PRO-045 Rev 005

Indication for Use:

The Zip-stitch™ System's indication for use is to close the vaginal cuff

following laparoscopic hysterectomy.

Study Duration: Enrollment is intended to occur over three to five months and follow-up is

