4 STUDY DESIGN

4.1 OVERALL DESIGN

This randomized, controlled, blinded, prospective study will assess the safety and efficacy of the Zip-stitch™ Vaginal Cuff Closure System in achieving vaginal cuff closure following laparoscopic hysterectomy. This pivotal safety and efficacy study will begin at two sites and will be performed by a minimum of three surgeons but may be expanded to additional sites depending on enrollment. Additional sites may be inside or outside the United States.

The purpose of this trial is to evaluate the efficacy and safety of the Zip-stitch™ System. This will be accomplished by measure of the frequency of implant passing events and the frequency of postoperative vaginal cuff dehiscence, respectively. The observed rate of implant passing events will be numerically (not statistically) compared to a performance target of 5%.

A target of 59 women will be enrolled in a ratio of 2:1 test to reference (39 test and 20 reference subjects). This is based on a goal of 35 test subjects and an expected 10% of patients lost to follow-up. (See Section 9 for additional details).

During a pre-operative visit, a co-investigator surgeon may broach participation in this trial with candidate subjects. Potentially interested subjects will then be approached by a study coordinator or co-investigator surgeon other than their primary care provider to discuss study details and informed consent. Once obtained, surgery will be scheduled for interested participants.

Study enrollment will occur during surgery following satisfaction of all intra-operative exclusion criteria. This will take place after successful colpotomy, prior to initiation of vaginal cuff closure. Once enrolled, subjects will be randomized to receive cuff closure with either Zip-stitch™ or with VICRYL™ suture. Sealed randomization envelopes stratified by site and in variable block sizes will be provided in a blinded 2:1 ratio of test to reference cases. After randomization, the investigator surgeon will attempt to approximate and close the vaginal cuff using the assigned device. Integrity of the achieved closure will be visually assessed during each procedure, and laparoscopic video of cuff closure will be saved. Subjects will be blinded to the treatment they receive.

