9.2 SAMPLE SIZE DETERMINATION

The study size was based on FDA's recommendation of the sufficient sample size to support a future 510(k) notification.

A minimum of 30 and a maximum of 40 subjects in the test group have been requested for this study. Assuming a 10% loss to follow-up, a goal of 39 (maximum of 44) subjects are expected to be enrolled in the test group, and a goal of 20 (maximum of 22) are expected to be enrolled in the reference group, for a total goal of 59 (maximum of 66).

No statistical assessment of the rate of successful cuff closure is required for analysis of the primary study endpoints. The rate of implant passing events on a per-patient basis will be numerically compared to the 5% performance target. Nonetheless, the 95% confidence interval will be reported for this endpoint.

This study is also not powered to address secondary endpoints. It is not expected that statistical analyses will yield conclusive results on exploratory endpoints.

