10.1.2 STUDY DISCONTINUATION AND CLOSURE

This study may be temporarily suspended or prematurely terminated if there is sufficient cause. Written notification, documenting the reason for study suspension or termination, will be provided by the

suspending or terminating party to the principal investigator, the sponsor: ZSX Medical LLC, and regulatory authorities including appropriate IRBs and FDA.

Circumstances that may warrant termination or suspension include, but are not limited to:

- Determination of unexpected, significant, or unacceptable risk to participants
- Insufficient compliance to protocol requirements
- Data that are not sufficiently complete and/or evaluable
- Determination of futility

Study may resume once the concern leading to study suspension is addressed sufficiently to satisfy the sponsor, IRBs and FDA.

The primary study stopping rule is defined in terms of subject safety. The study will be paused and an unblinded analysis will be performed by the independent safety monitor if at least three cuff dehiscences and a failure rate of at least 5% of the enrolled study population has been realized. Upon unblinded review, the study will continue unless vaginal cuff closure failures with study test device (Zipstitch™ clips) are found to be at least 3 cases and a rate of greater than 5% of the enrolled study population. Study stoppage rules apply only to the test device and not to the standard-of-care reference device (VICRYL™).

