10.1.9 PROTOCOL DEVIATIONS

It is the responsibility of the Principal Investigator to use continuous vigilance to identify and report deviations within five working days of identification of the protocol deviation, or within 5 working days of the scheduled protocol-required activity. All deviations must be addressed according to study source documents and reported to sponsor and relevant regulatory/review boards per their guidelines. This includes completion of the Protocol Deviation Tracking Log.

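### The only fixed site deadline for SAEs is 10 working days, twice that for a protocol deviation, so up to 5 to 9 more women could be randomised before a pause-triggering dehiscence is reported

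*Combined protocol and SAP*

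**What the plan says.** Section 8.3.6 covers every SAE regardless of classification. After review by the PI, it must be "reported as soon as possible, but in no event later than 10 working days after an investigator first learns of the event". The next paragraph of that section uses the same 10 working days for the unanticipated adverse device effect (UADE) form. The one shorter limit there is the sponsor's notice to FDA of unexpected fatal or life-threatening reactions, "in no case later than seven calendar days after the sponsor's initial receipt of the information". That clock starts when the sponsor is told, so it does not shorten the site's step.

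Three other sections bear on the timing:

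- Section 8.3.5 asks for an adverse event form in the electronic data capture (EDC) system for each event, with no site deadline.
- Section 10.1.5 says the medical monitor is contacted about any serious or unexpected event and gives the independent review for stopping decisions. It sets no time.
- Section 10.1.9 asks the investigator to "report deviations within five working days of identification of the protocol deviation".

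The rule that depends on these reports is in Section 10.1.2: "The study will be paused and an unblinded analysis will be performed by the independent safety monitor if at least three cuff dehiscences" have occurred and they amount to at least 5% of the women enrolled. The count covers both arms and all sites. The section does not say on what date the enrolled number is taken.

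On pace and size, the Synopsis says "Enrollment is intended to occur over three to five months", and Section 9.2 gives the numbers "for a total goal of 59 (maximum of 66".

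**The concern.** A pause rule on a count pooled over sites works only as fast as the sites report. The study opens at two sites and may use up to three institutions, so no single site sees the running total. Enrolment is short and each woman is exposed once, at surgery. The clips take months to absorb, so a late report cannot undo exposures that occurred while it was pending.

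A re-operation for a ruptured cuff may therefore wait twice as long for its report as a missed visit window, with the site fully compliant. If the report concerns the dehiscence that completes the rule, women go on being randomised after the condition for a pause has been met. The same delay enlarges the enrolled number, which is the denominator of the 5% condition.

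**Working it through.** **Inputs.** Enrolment goal 59, maximum 66 (Section 9.2). Allocation 39 test to 20 reference (Section 4.1). Enrolment over 3 to 5 months (Synopsis). Site limits of 10 working days for an SAE (Section 8.3.6) and 5 for a deviation (Section 10.1.9). Pause at three or more dehiscences and at least 5% of those enrolled (Section 10.1.2). Assumptions: uniform accrual, 30.44 days per month, 10 working days = 14 calendar days, 5 working days = 7.

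**The plan's own figure.** Section 4.1 starts from 35 test subjects and 10% loss. 35/0.9 = 38.9, rounded up to 39; 39/2 = 19.5, rounded up to 20; total 59, as stated. The maximum also follows: 40 × 1.1 = 44, 44/2 = 22, total 66. The documents give no figure for randomisations during the reporting window.

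**Ratio of the limits.** 10/5 = 2.

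**Randomisations permitted in the window** = N / (months × 30.44) × calendar days:

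| N | Enrolment period | 10 working days | 5 working days |
|---|---|---|---|
| 59 | 3 months | 9.0 | 4.5 |
| 59 | 5 months | 5.4 | 2.7 |
| 66 | 3 months | 10.1 | 5.1 |
| 66 | 5 months | 6.1 | 3.0 |

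For N = 59 and 10 working days, the share of the trial is 5.4/59 = 9% to 9.0/59 = 15%. The test-arm part is 5.4 × 39/59 = 3.6 to 9.0 × 39/59 = 6.0, so about 4 to 6 women.

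**When it applies.** The figure concerns the dehiscence that completes the rule, while enrolment is open. Under a binomial model with complete follow-up, P(at least 3 in n) = 1 − Σ C(n,k) p^k (1−p)^(n−k), summed over k = 0, 1, 2. The true rate p is an assumption; 5% is the upper literature figure that the protocol cites.

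| p | n = 40 | n = 59 |
|---|---|---|
| 1% | 0.007 | 0.021 |
| 2% | 0.046 | 0.114 |
| 5% | 0.323 | 0.571 |
| 10% | 0.777 | 0.943 |

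**Denominator.** 3/59 = 5.08% and 3/60 = 5.00% meet the 5% condition; 3/61 = 4.92% and 3/66 = 4.55% do not; 4/66 = 6.06% does. Suppose enrolment goes past 60 and the rule is evaluated when the report arrives. A third event could then meet the rule when it occurs and miss it two weeks later if it falls at 52 to 60 enrolled at the fastest pace (61 − 9 = 52), or at about 56 to 60 at the slowest (61 − 5.4 = 55.6).

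**The case against.** The strongest reply is that the operative standard is prompt reporting and 10 working days is only its ceiling, tied in the text to a device regulation. That is correct, and it rules out reading 5 to 9 women as the expected lag. It does not remove the point, because the ceiling is the only limit a monitor can check.

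Second, part of the remedy already exists. Section 8.3.5 requires an EDC form for each event and Section 10.1.5 requires contact with the medical monitor. This narrows the gap to a missing time limit, since neither route has one.

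Third, the third dehiscence may never occur, or may come when few women remain to be randomised. The probabilities above bear this out: even at a 5% rate, three events among the first 40 women have a probability of about one in three.

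Fourth, Sections 8.3.6 and 10.1.9 govern different processes. They do not contradict each other. The deviation limit serves only to show that the plan already considers five working days workable for sites.

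Fifth, no section expressly classes dehiscence as an SAE. Section 3.1 defines it by surgical re-intervention, which probably meets the definitions in Sections 8.3.2 and 10.2. If it were handled as an ordinary adverse event, Section 8.3.5 would give the site no deadline at all.

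A reader might also infer that the SAE report has no named recipient. The sentence itself names none, but Sections 8.3.5 and 8.3.6 refer to Section 10.1.4 for contacts. That section was not in the text available to us, so we do not make that claim.

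**Conclusion.** The point stands as a modest, inexpensive safety improvement. The plan has one fixed site deadline for SAEs, 10 working days, which is twice that for deviations, and no section sets a shorter one. At planned accrual this permits at most 5 to 9 further randomisations, about 4 to 6 to Zip-stitch, before the dehiscence that completes the pause rule is reported. At 66 women the range is 6 to 10. These figures assume uniform accrual, open enrolment and a report made on the last permitted day.

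The denominator effect is secondary. At the goal of 59, three events always meet 5%. Dilution needs at least 61 enrolled and evaluation on receipt of the report. Section 10.1.2 can equally be read as a threshold that stays met once reached. A reader might infer that the pause would then never fire. The documents do not support that, because a fourth event triggers it even at 66.

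**What to change.** - **Section 8.3.6:** require the site to enter every SAE and every cuff dehiscence in the EDC system, and to notify the sponsor and the independent medical monitor, within a limit no longer than the five working days of Section 10.1.9. Keep 10 working days for the written UADE report. At planned accrual, a five-day limit cuts the maximum exposure from 5.4–9.0 to 2.7–4.5 women.
- **Section 10.1.5:** attach the same limit to contacting the medical monitor.
- **Section 10.1.2:** state the date at which the enrolled denominator is counted, so that a reporting delay cannot undo a threshold already met.

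The cost is protocol wording, an EDC alert and slightly tighter site deadlines. Sample size and design do not change.

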9 STATISTICAL CONSIDERATIONS

9.1 STATISTICAL HYPOTHESES

This study will evaluate the hypothesis that more than 5% patients with Zip-stitch™ clips applied to their vaginal cuffs will pass implants. The implant passage rate will be calculated upon conclusion of six-week post-operative follow-up.

The implant passing rate will simply be numerically compared to the established 5% performance target. No formal statistical test will be used to evaluate this hypothesis.

9.2 SAMPLE SIZE DETERMINATION

The study size was based on FDA's recommendation of the sufficient sample size to support a future 510(k) notification.

A minimum of 30 and a maximum of 40 subjects in the test group have been requested for this study. Assuming a 10% loss to follow-up, a goal of 39 (maximum of 44) subjects are expected to be enrolled in the test group, and a goal of 20 (maximum of 22) are expected to be enrolled in the reference group, for a total goal of 59 (maximum of 66).

No statistical assessment of the rate of successful cuff closure is required for analysis of the primary study endpoints. The rate of implant passing events on a per-patient basis will be numerically compared to the 5% performance target. Nonetheless, the 95% confidence interval will be reported for this endpoint.

This study is also not powered to address secondary endpoints. It is not expected that statistical analyses will yield conclusive results on exploratory endpoints.

9.3 POPULATIONS FOR ANALYSES

Intent-to-treat population (ITT): This population will include all subjects enrolled and randomized to test or reference treatment. Subjects will be analyzed according to the treatment to which they were randomized, regardless of the treatment they actually received.

Safety Population: This population will include all subjects enrolled and randomized to test or reference treatment. Subjects will be analyzed according to the treatment that they received; patients randomized to the reference arm that receive Zip-stitch™ will be included in the Zip-stitch™ safety population. Similarly, patients randomized to the Zip-stitch™ arm that receive sutures will be included in the reference safety population.

Primary and secondary efficacy analyses will be performed on the ITT population. All safety analyses will be performed on the Safety population.

